7.3.7. Sensitivity Analyses

To assess the robustness of the primary analysis, the following sensitivity analyses of the primary endpoint will be conducted at Week 24/EOT.

7.3.7.1. Sensitivity Analysis 1

To assess the potential impact of unvalidated feminine product use, the primary endpoint will be analyzed as sensitivity analysis in a similar fashion to the primary analysis using the Week 24/EOT validated MBL volume (obtained from the validated or validated-but-unauthorized feminine products only and excluding unvalidated products).

7.3.7.2. Sensitivity Analysis 2

To assess the potential impact of missing data due to inadequate collection of feminine products, the primary endpoint will be analyzed with a sensitivity analysis using the missing data handling rules as described in [Table 8](#) below where the observed MBL volume will be used to assess the responder status at Week 24/EOT when feminine product collection was incomplete. These rules differ from those used in the primary analysis in that no imputation will be implemented for patients with < 100% feminine product compliance and the reported MBL volume both < 80 mL and a \geq 50% reduction from Baseline as highlighted in [Table 8](#).

Table 8: Derivation of Responder Status at Week 24/EOT and Missing Data Handling Rules – for Sensitivity Analysis

Treatment Exposure	FP Collection (FPRR)	Observed MBL Volume	Reason for No FP Collection	Responder Status
< 4 weeks	N/A	N/A	N/A	Imputed as non-responder
\geq 4 weeks	100% FP Compliance	N/A	N/A	Based on the observed MBL volume
	< 100% FP Compliance	MBL volume \geq 80mL or < 50% reduction from Baseline	N/A	Imputed as non-responder based on the observed MBL volume
		MBL volume < 80mL and \geq 50% reduction from Baseline	N/A	Based on the observed MBL volume
No FP Collection	N/A	Reported “Amenorrhea”	Reported “Amenorrhea”	Imputed as responder
			Reported “Spotting or negligible bleeding” and confirmed by eDiary ^a	Imputed as responder
		Reported “Spotting or negligible bleeding” although not confirmed by eDiary or any other reason, had at least 8 weeks of MBL volume data	Based on the imputed MBL volume	
		The entries in the eDiary did not verify “Spotting or negligible bleeding” or any other reason and if had < 8 weeks of MBL volume data	Imputed as non-responders	

Abbreviations: eDiary, electronic diary; FP, feminine product; EOT, end of treatment; MBL, menstrual blood loss; N/A, not available.

^a Defined as those patients who meet the following criteria: eDiary entry rate $>70\%$ and no more than 3 consecutive days and no more than 5 days of bleeding/spotting and use of feminine product reported on the eDiary over the Week 24/EOT visit window (see Table 5).

7.3.7.3. Sensitivity Analysis 3

To assess the potential impact of early discontinuation on the primary endpoint, the primary endpoint will be analyzed with a sensitivity analysis defining the patients' responder status as follows:

- Patients who discontinued study drug during the first 4 weeks for any reason or who discontinued study drug between Week 4 and Week 12 due to an adverse event, surgery or other intervention for heavy menstrual bleeding, reported lack of efficacy, or bleeding complaints will be considered as non-responders;
- All other patients will have their responder status defined using data from the Week 24/EOT assessment period using the last observation carried forward method.

7.3.7.4. Sensitivity Analysis 4

To assess the potential impact of the length and full exposure of the treatment, the primary endpoint will be analyzed for the Completers population as a sensitivity analysis. The Completers population is defined as patients in the mITT population who completed 24 weeks of study treatment.

7.3.7.5. Sensitivity Analysis 5

The primary endpoint will be analyzed on the Per-Protocol population as a sensitivity analysis, using the methods specified for the primary analysis (see definition of Per-Protocol population in Section 4.2.2).

7.3.7.6. Sensitivity Analysis 6

As a sensitivity analysis to the primary analysis using the mixed-effects model for imputing missing MBL volumes at Week 24/EOT, multiple imputation approach will be implemented as described below.

A multiple imputation method (Rubin, 1987; von Hippel, 2018) will be used to impute missing or partially missing MBL volume identified by the missing data handling rules (see Table 7 and Table 8) at Week 24/EOT as described in the following 5 steps. In this method, an arbitrary missing pattern will be assumed using Markov Chain Monte Carlo imputation to generate a monotone missing pattern for the observed longitudinal MBL volume values (including 0 mL if the patient has amenorrhea). Imputation will be performed separately by randomized treatment group (Sullivan, 2018), given the distinct bleeding patterns among the three treatment groups.

Normalizing transformations will be applied to the statistics estimated from each imputed dataset before the Rubin's combination rules can be applied (Ratitch, 2013). This combined estimation and statistical test will account for the additional variability due to imputation to provide a robust assessment of the treatment effect.

- Step 1: Identifying patients with missing or incomplete MBL volume from the longitudinal MBL volume dataset as collected.
- Step 2: Generating a monotone missing pattern using the Markov Chain Monte Carlo technique by imputing missing MBL volume measurements that are between non-missing results.

Step 3: Imputing the remaining missing values $m = 100$ times using a regression model; therefore, generating 100 complete longitudinal MBL volume datasets.

Note: if a patient missed Week 8 and prematurely discontinued study drug (eg, at Week 20) and MBL volume at Week 20 is missing or partially missing, MBL volume will be imputed for intermittent missing data at Week 8, Week 20 (EOT), and Week 24 due to discontinuation.

Step 4: Performing the same CMH test pre-specified for the primary endpoint analysis and estimating the responder rates for each arm using each of the 100 datasets based upon the MBL volume at Week 24/EOT.

Note: in the example above, the imputed MBL volume at Week 20 (EOT) will be used in the analysis, although MBL volume is imputed at Week 24.

Step 5: Combining the results from the 100 complete datasets to make inferences about the treatment effect on the responder rate.

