7.3.3. Definitions Related to Menstrual Blood Loss

Menstrual Blood Loss Volume

All returned feminine products (validated, validated but unauthorized, or unvalidated products) collected at each visit will be analyzed by the alkaline hematin method to obtain the MBL volume. The MBL volume measured over the Week 24/EOT feminine product collection interval (up to 35 days prior to the last dose of treatment) will be used for analysis of the primary efficacy endpoint (see details below). The vendor, KCAS, reports when unauthorized feminine products (products not dispensed for use in the trial) have been returned. KCAS also reports whether the unauthorized products have previously been validated for their analysis. The report details MBL volumes for authorized, unauthorized but validated, and unauthorized and unvalidated products.

Validated Menstrual Blood Loss Volume

All returned feminine products collected at each visit, with the exception of unvalidated products, will be assessed by the alkaline hematin method to obtain the validated MBL volume. The validated MBL volume is derived from assessments of all returned validated feminine products (including validated and validated but unauthorized products) and will be used for sensitivity analysis.

Baseline Menstrual Blood Loss Volume

Baseline MBL volume is defined as the average MBL volume from the one or two consecutive screening menstrual cycles used to meet the inclusion criteria prior to the date of the first dose of study drug as assessed by the alkaline hematin method as follows:

For patients with MBL volume \geq 160 mL during the screening period, the Baseline MBL volume is the last measurement collected before the first administration of study drug.

If the MBL volume is $<$ 160 mL, the Baseline MBL volume is defined as the average of the MBL volume from the two screening menstrual cycles used to meet the inclusion criteria prior to the date of the first dose of study drug as assessed by the alkaline hematin method (see Figure 4-2 of the study protocol for details).

Week 24/EOT Feminine Product Collection Interval

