To quantify degree of compliance with feminine product collection, the FPRR will be calculated based on the inventory of feminine product returned by day (dates) summarized on the Feminine Product Collection eCFR page (provided by the vendor, KCAS) and responses to the eDiary Question 4 regarding bleeding experience and Question 5 regarding the use of feminine product obtained for the corresponding eDiary window (see [Table 5](#)). Specifically:

- For those who returned feminine product at Week 24/EOT, the FPRR was calculated as the observed number of days with returned feminine products (based on the inventory of FP received by KCAS) divided by the expected number of days with bleeding and use of product as reported on the eDiary within the Week 24/EOT feminine product collection interval (as defined above).
- For those who did not return any feminine products:
 - If the reason was amenorrhea reported on the eCRF or if spotting/negligible bleeding was reported on the eCRF and confirmed by eDiary over the Week 24/EOT visit window, their FPRR will be set to 100% because the lack of menstruation obviates the need for feminine product collection.
 - Otherwise if the reason is any other, their FPRR was set to 0.

$$\text{FPRR} = \frac{\text{observed (No. of days with returned FP [per KCAS])}}{\text{expected (No. of days reported bleeding and use of FP [per eDiary])}} \times 100$$

Return of feminine products will be summarized in the CSR for Week 24/EOT visit.

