7.3.5. Derivation of Responder Status at Week 24/EOT and Missing Data Handling Rules

For the evaluation of primary endpoint, missing data handling rules will be implemented for deriving responder status at Week 24/EOT as described below. The following elements will be checked: duration of treatment exposure; compliance with feminine product collection against the eDiary, as measured by FP RR; compliance with eDiary entry, defined as the proportion of eDiary entry days over the length (days) of FP collection interval for Week 24/EOT visit; and reasons for no FP collection (as displayed in [Table 7](#)).

Patients with < 4 weeks of treatment who withdraw from the study prematurely due to lack of efficacy or withdraw from the study prematurely to undergo surgical intervention for uterine fibroids will be considered as non-responders.

All other patients will have their responder status determined as follows:

- For patients with a FP RR of 100%, responder status will be determined based on the observed MBL volume;
- For patients who had incomplete feminine product collection, with a FP RR of < 100%, responder status will be derived based on either imputed or observed MBL volume;
 - Those with an MBL volume \geq 80 mL or < 50% reduction from Baseline will be considered as non-responders;
 - Those with an MBL volume < 80 mL and \geq 50% reduction from Baseline will be imputed for partial or complete missing MBL volume (see Section [7.3.6](#) for details).
- For patients who did not return a feminine product collection, responder status will be determined depending on the reason reported on the Feminine Product Collection eCRF:
 - If the reason is reported as Amenorrhea, the last 35 days of treatment will be used to derive responder status:
 - If the Week 24/EOT interval was 35 days, then she will be considered as a responder;
 - If the Week 24/EOT interval was <35 days, the following supportive information will be used to derive responder status:
 - If a patient reported amenorrhea at the visit prior to Week 24/EOT, she will be defined as a responder;
 - If a patient did not report amenorrhea at the visit prior to Week 24/EOT, eDiary data from the prior visit interval will be reviewed to confirm whether the patient was amenorrheic for a total of 35 days.

- If the eDiary from the previous interval confirms amenorrhea, then the patient will be considered as a responder;
- Otherwise, MBL volume will be imputed.

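### Sensitivity Analysis 1 drops the blood on unvalidated products but not their collection days, so at a 100% return rate that blood is scored as 0 mL and only over-reading is tested

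*SAP*

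**What the plan says.** Four rules in the SAP bear on this point.

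- **Primary volume (section 7.3.3).** Unvalidated products are included: "All returned feminine products (validated, validated but unauthorized, or unvalidated products) collected at each visit will be analyzed by the alkaline hematin method".
- **Validated volume (section 7.3.3).** "All returned feminine products collected at each visit, with the exception of unvalidated products, will be assessed by the alkaline hematin method". Nothing is put in place of the volume left out.
- **Sensitivity Analysis 1 (section 7.3.7.1).** The endpoint is analysed "in a similar fashion to the primary analysis using the Week 24/EOT validated MBL volume", that is, the volume "obtained from the validated or validated-but-unauthorized feminine products only and excluding unvalidated products". The section changes neither the FPRR nor Baseline MBL.
- **FPRR (section 7.3.3) and its use (section 7.3.5, Table 7).** The numerator is the "observed number of days with returned feminine products (based on the inventory of FP received by KCAS"), and the denominator is the "expected number of days with bleeding and use of product as reported on the eDiary". Neither depends on whether a product was validated. At full return no imputation takes place: "For patients with a FP RR of 100%, responder status will be determined based on the observed MBL volume". Below 100%, a woman whose volume fails either criterion is a non-responder, and one whose volume passes both is imputed.

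The file holds two versions of the SAP, Amendment 1 and the version before it. Both carry these rules in the same form.

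**The concern.** The doubt about an unvalidated product is whether its reading is right. The true loss on that product is therefore uncertain and could be higher or lower than measured. Sensitivity Analysis 1 sets it to zero and still accepts the day as fully collected.

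This does not fit the SAP's own treatment of incomplete collection. When a day's product was not returned, section 7.3.5 does not accept a low volume at face value and sends the woman to imputation. When a day's blood was measured and then removed by rule, the low volume is accepted.

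What is at stake is how the result is read. Sensitivity Analysis 1 is the only one of the six sensitivity analyses aimed at product validation. If it agrees with the primary analysis, a reader will take that as evidence that unvalidated products do not matter. It supports that conclusion only for products that read too high.

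**Working it through.** **Plan figures.** The SAP gives no figure for this analysis and does not state the share of unvalidated products. The only planning figures used below are the 25% placebo response rate and the 30-point difference in section 2.2.1. The power stated there, at least 99%, reproduces: 130 × 0.8 = 104 evaluable women per arm at 55% versus 25% gives 0.995. The rates are taken as they stand.

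**Notation.** For one woman at FPRR 100%, let B be Baseline, T the total Week 24/EOT volume, U the part on unvalidated products, and V = T − U the validated volume. By section 7.3.4, a volume x is a response if x < 80 mL and (B − x)/B ≥ 50%.

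**Direction.** U ≥ 0, so V ≤ T. Both criteria become easier as x falls. With B fixed, a woman who responds on T must respond on V. She changes status only if T fails at least one criterion and V passes both. There are two routes, shown with assumed volumes:

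- **Total of at least 80 mL.** B = 150, T = 60 + 45 = 105: non-responder. V = 60, and (150 − 60)/150 = 60%: responder.
- **Total below 80 mL but reduction below 50%.** B = 100, T = 60, and (100 − 60)/100 = 40%: non-responder. V = 40, and (100 − 40)/100 = 60%: responder.

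Extreme case: B = 150 and T = U = 120. The total fails, V = 0 mL, and she is a responder. Not every woman changes: with B = 200, T = 100 and U = 10, V = 90 mL and she stays a non-responder.

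**Check by simulation.** The rules were applied to 400,000 random combinations of Baseline, total volume and unvalidated share at FPRR 100%. Of these, 138,937 moved from non-responder to responder and 0 moved back. The first count depends on the assumed distributions. The zero does not, because V ≤ T.

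**Women not judged on observed volume.** At FPRR < 100%, the only change in the same cases was from non-responder to imputed. For women imputed in both analyses, refitting the model with validated Week 24 volumes moved 97 of 3,000 towards response and 5 away from it, in an illustrative run with assumed parameters.

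**Effect on the treatment difference.** Assume that a share f of non-responders changes status. Active becomes 0.55 + 0.45f and placebo 0.25 + 0.75f. With f = 10%:

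| Where women change | Active | Placebo | Difference |
|---|---|---|---|
| Nowhere | 55.0% | 25.0% | 30.0 points |
| Both arms | 59.5% | 32.5% | 27.0 points |
| Placebo only | 55.0% | 32.5% | 22.5 points |
| Active only | 59.5% | 25.0% | 34.5 points |

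**The case against.** The strongest reply is that section 7.3.7.1 does not say outright that days with unvalidated products still count as returned. It says only that the analysis resembles the primary one, and a programmer might rebuild the FPRR on validated products. It is true that the mechanism is inferred. But the only FPRR definition in the SAP has no such restriction, and the section changes nothing except the volume. Carried out as written, the rules give the result shown.

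A second reply is that comparing results with and without the unvalidated volume is informative. That stands in part. If unvalidated products read too high, the analysis shows what follows from removing them. It cannot show the reverse: a woman below the thresholds only because such a product under-read stays below them after subtraction.

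Three further readings are tempting, and the documents do not support them.

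- **A reader might infer that the analysis favours the drug.** Changes come from non-responders, who are 75% of placebo and 45% of active under the planning rates. Equal rates of change therefore shrink the difference, from 30 to 27 points. Inflation would need changes concentrated in the active arm, and nothing in the SAP points to that.
- **A reader might infer that no woman can ever move away from response.** That is exact only for status set by observed volume with Baseline unchanged. Imputed women can occasionally move the other way.
- **A reader might infer that the trial's main result is in doubt.** The primary analysis counts all returned products and is not touched.

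**Conclusion.** The point holds as a defect in one sensitivity analysis. As written, blood measured on unvalidated products is scored as 0 mL in women with an FPRR of 100%. Among women judged on observed volume, the analysis can then only turn non-responders into responders. It is a one-sided check, valid for over-reading and blind to under-reading.

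This rests on two things: that the FPRR definition in section 7.3.3 applies unchanged, which is inferred, and that Baseline MBL is not restricted to validated products, since section 7.3.7.1 replaces only the Week 24/EOT volume. The size in this trial cannot be determined from the SAP, because the frequency of unvalidated products is not given. The illustrative range of 22.5 to 34.5 points around the planned 30 assumes that 10% of non-responders change status in one or both arms. It shows that the direction is open. The change should be made, but no confirmatory conclusion depends on it.

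**What to change.** In section 7.3.7.1, state that any Week 24/EOT collection containing unvalidated product volume is treated as incomplete (FPRR < 100%). The existing Table 7 rows then apply: non-responder if the validated volume alone is at least 80 mL or the reduction is below 50%, otherwise imputed. In the first example above, the woman with 60 mL validated would be imputed. Observed-volume responders with unvalidated products would also be imputed or tested on the same rows, so movement in both directions becomes possible.

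Add one bounding run that scores every woman with any unvalidated product at Week 24/EOT as a non-responder. It needs no modelling.

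Apply the rule to the whole collection, not by day. Section 7.3.3 says that the vendor reports volumes by product class, but the SAP does not show that product class is available by day. Leave Baseline MBL unchanged: restricting it as well would alter the percent-reduction criterion and could put some women below the entry volume.

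The cost is one changed derivation and one extra run on volumes that the vendor already reports. The downside is a few more imputed values in one sensitivity analysis.

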7.3.8. Subgroup Analyses

Subgroup analyses of the primary efficacy endpoint comparing the relugolix + E2/NETA group versus the placebo group will be performed to assess whether treatment effects are consistent across clinically important subgroups. The odds ratio and its 95% CI based on a logistic regression model will be displayed in a forest plot for each subgroup. The logistic regression model will include treatment group, Baseline MBL volume value and geographic region as covariates. Subgroups will include, but will not be limited to, the subgroups outlined in [Table 9](#).

Table 9: Planned Subgroup Analyses

Subgroup Name	Subgroup Level
Geographic region	North America vs Rest of World
Menstrual blood loss volume at Baseline (mL)	< 225 vs ≥ 225 < 120, 120 to < 160, 160 to < 225, ≥ 225
Age category (years)	< 40 vs ≥ 40 < 35, 35 to < 40, 40 to < 45, ≥ 45
Race	Black or African American vs Not Black or African American; Black or African American, White, Other
Volume of myoma at Baseline (cm ³)	< 25 vs ≥ 25
Volume of uterus at Baseline (cm ³)	< 300 vs ≥ 300
BMI (kg/m ²) at Baseline	< 30 vs ≥ 30 < 25, 25 to < 30, 30 to < 35, 35 to < 40, ≥ 40
Maximum NRS score for uterine fibroid-associated pain at Baseline	< 4 vs ≥ 4
History of prior pregnancy	Yes/No

Abbreviations: BMI = body mass index; NRS = Numerical Rating Scale.

7.4. Secondary Efficacy Endpoints

Secondary efficacy variables include seven key secondary endpoints with alpha-protection and other secondary endpoints. All secondary efficacy endpoints and analyses are summarized in [Appendix 1](#).

The treatment effect of relugolix + E2/NETA (Group A) compared to placebo (Group C) will be tested for the alpha-protected secondary endpoints using a gate-keeping procedure (see Section [7.4.1](#)).

Comparative statistics (p-values, 95% CIs for differences) will be provided for treatment comparison of the relugolix + E2/NETA group with the placebo group for all other secondary efficacy endpoints. Treatment difference between the relugolix + delayed E2/NETA group and the placebo group will be formally tested only for the primary efficacy endpoint. There will be no statistical testing for treatment differences between the relugolix groups (relugolix + E2/NETA group against relugolix + delayed E2/NETA group) for any efficacy endpoint (see Section [7.4.2](#)).

7.4.1. Key Secondary Efficacy Endpoints with Alpha-Protection

For testing whether relugolix + E2/NETA (Group A) is statistically significantly superior to placebo (Group C) for the primary efficacy endpoint as well as the seven key secondary endpoints listed below, a gate-keeping mixed sequence testing procedure will be applied to maintain the family-wise type I error rate. Under this testing procedure, the primary endpoint

Statistical Analysis Plan

[figure not shown]
Amendment 1: Effective June 14, 2019

MVT-601-3001 and 3002

[figure not shown]
will be tested first at a 2-sided 0.05 significance level. If the p-value for primary endpoint is < 0.05 , the seven key endpoints listed below will be tested sequentially in the order depicted in [Figure 3 \(LIBERTY 1\)](#) and [Figure 4 \(LIBERTY 2\)](#).

For the relugolix + E2/NETA group to be considered statistically superior to the placebo group on a secondary endpoint, the two-sided p-value must be < 0.05 for that secondary endpoint and for all higher-ranking secondary endpoints, as well as for the primary endpoint. If the two-sided p-value is < 0.05 for the fourth endpoint (proportion of women with hemoglobin ≤ 10.5 g/dL at Baseline who achieve an increase of > 2 g/dL from Baseline at Week 24 for LIBERTY 1; proportion of women who achieve a maximum NRS score ≤ 1 for uterine fibroid-associated pain over the last 35 days of treatment in the subset of women with a maximum pain score ≥ 4 during the 35 days prior to randomization for LIBERTY2), the remaining three endpoints (the fifth, sixth, or seventh) will be tested using the Hochberg step-up procedure.

Figure 3: Mixed Sequence Testing Procedure for Primary and Key Secondary Endpoints in LIBERTY 1

Abbreviations: BPD = Bleeding and Pelvic Discomfort; EP = endpoint; Hgb = hemoglobin; max = maximum; MBL = menstrual blood loss; M-vol = myoma volume; NRS = Numerical Rating Scale; PE = primary endpoint; Prop = proportion; UFS-QoL BPD = Uterine Fibroid Symptom and Health-Related Quality of Life Bleeding and Pelvic Discomfort; U-vol = uterine volume.

Figure 4: Mixed Sequence Testing Procedure for Primary and Key Secondary Endpoints in LIBERTY 2

Abbreviations: BPD = Bleeding and Pelvic Discomfort; EP = endpoint; Hgb = hemoglobin; max = maximum; MBL = menstrual blood loss; M-vol = myoma volume; NRS = Numerical Rating Scale; PE = primary endpoint; Prop = proportion; UFS-QoL BPD = Uterine Fibroid Symptom and Health-Related Quality of Life Bleeding and Pelvic Discomfort; U-vol = uterine volume.

From the Hochberg procedure, the p-values will be calculated for the three endpoints (5, 6, and 7) and ranked from the smallest to the largest. The endpoint corresponding to the largest p-value gets tested first. If the p-value is < 0.05 , then no further testing will occur, and it will be concluded that all three endpoints are positive. Otherwise, the endpoint corresponding to the second largest p-value will be tested. If the p-value is < 0.025 , then no further testing will occur, and it will be concluded that the endpoints corresponding to the middle and smallest p-values are positive. Otherwise, the endpoint with the smallest p-value will be tested. If the p-value is < 0.0167 , no further testing will occur, and it will be concluded that only the endpoint with the smallest p-value is positive. Otherwise, all three endpoints did not pass the statistical significance criterion at 0.05 level.

The seven key secondary efficacy endpoints are as follows:

1. Proportion of women who achieve amenorrhea over the last 35 days of treatment;
2. Percent change from Baseline to Week 24 in MBL volume;

- 3. *Change from Baseline to Week 24 in Bleeding and Pelvic Discomfort Scale score as measured by the UFS-QoL Symptom Severity Scale (Q1, Q2, Q5);*
- 4. *Proportion of women with a hemoglobin ≤ 10.5 g/dL at Baseline who achieve an increase of > 2 g/dL from Baseline at Week 24*
- 5. *Proportion of women who achieve a maximum NRS score ≤ 1 for uterine fibroid associated pain over the last 35 days of treatment in the subset of women with a maximum pain score ≥ 4 during the 35 days prior to randomization;*
- 6. Percent change from Baseline to Week 24 in uterine fibroid volume;
- 7. Percent change from Baseline to Week 24 in uterine volume.

For key secondary efficacy endpoints (1, 4, and 5) that are evaluating proportions, treatment comparisons will be performed using a stratified Cochran-Mantel-Haenszel test with the randomization stratification factors as strata. Point estimates and 2-sided 95% CIs for treatment differences in proportions will be provided.

For key secondary endpoint 4, an increase in hemoglobin of 2g/dL is considered clinically meaningful, because it corresponds to approximately the same increase as that expected after a transfusion of ~ 2 units of packed red blood cells (Man, 2016; Bachowski, 2017).

For deriving the key secondary endpoint 5 (proportion of women who achieve a maximum NRS score ≤ 1 for uterine fibroid-associated pain over the last 35 days of treatment in the subset of women with a maximum pain score ≥ 4 during the 35 days prior to randomization), the patient subset and Week 24/EOT maximum value are determined as follows.

Because patients were asked to begin eDiary entries after returning the first collection of feminine products, the number of eDiary entries made during screening varies with the duration of screening for each patient. Some patients required only one collection to be randomized, whereas others required as many as four collections to confirm eligibility.

Once the qualifying menstruation was completed and the patient qualified for randomization based upon resulting MBL volume(s), the recording of patient's NRS scores for screening phase will be ended and the number of pain score days at Baseline can be as short as 7 days or as long as 70 days prior to randomization. If a patient meets the subset definition (maximum NRS score ≥ 4 at Baseline) over a portion of the screening days (eg, 7-70 days), she will also meet the subset definition on the entire 35 days interval.

Since the maximum NRS value is used to determine inclusion into the subset rather than an average NRS value, the variable number of days for inclusion of patients has no major impact on determining patient subset. To ensure robust estimate of response, the minimum number of non-missing daily pain scores required to calculate the maximum score at Week 24/EOT is at least 28 days (80% of the last 35 days of treatment) of pain scores recorded in the e-Diary entry.

The primary analysis of key secondary endpoint 5 will be analyzed for the subset of women who have a maximum pain score ≥ 4 during the 35 days prior to randomization and who have at least 28 days (80% of the last 35 days of treatment) of pain scores recorded in the e-Diary at Week 24/EOT. In addition, a sensitivity analysis will be conducted on the subset of women who have

Statistical Analysis Plan
Amendment 1: Effective June 14, 2019

MVT-601-3001 and 3002

a maximum pain score ≥ 4 during the 35 days prior to randomization without restricting number of days of pain scores recorded in the e-Diary.

The analysis for endpoint 5 (proportion of women who achieve a maximum NRS score ≤ 1 for uterine fibroid-associated pain over the last 35 days of treatment in the subset of women with a maximum pain score ≥ 4 during the 35 days prior to randomization) will also be performed using NRS scores reported on eDiary during menstrual and non-menstrual days.

For key secondary efficacy endpoints (6 and 7) evaluating percent change from Baseline in uterine fibroid volume and uterine volume that are measured only at Week 24, an analysis of covariance (ANCOVA) model will be used to assess treatment effect with treatment, randomization stratification factors and Baseline value as covariates.

For key secondary efficacy endpoints (2 and 3) evaluating the change (absolute or % change) from Baseline to Week 24, treatment comparisons will be performed using a mixed model repeated measures approach with treatment, visit, randomization stratification factors and treatment by visit interactions included as fixed effects and random effects (from the individual patients). In this model, an unstructured variance-covariance matrix is assumed for each patient.

